- **Subject Medication Diary**

All enrolled (i.e., randomized patients) will be asked to maintain a "Subject Medication Diary". This template diary will be provided during the Baseline/Randomization visit to keep track of the daily doses and of the timing of study medications. Patients will be asked to bring this diary along with the study medication bottles to the Day 7 and Day 14 study visits to assess for compliance and drug accountability. If this is not done at the Day 14 visit for any reason, this can also be completed at Day 28 visit.

4.6.2 TIMING OF STUDY ASSESSMENTS (SEE APPENDIX 1)

The patients willing to participate in the study will only be included when all screening examination procedures have demonstrated that all inclusion criteria and none of the

exclusion criteria apply. The patients will be assigned a patient number within the study.

Screening (Visit 1, Day -14 to Day -1)

During the screening visit the following assessments will be performed:

- Informed consent to be obtained from the patient, parent or legal guardian .
- Eligibility criteria including all inclusion and exclusion criteria.
- Demographics .
- Medical history: including all clinically significant diseases, prior medical interventions (e.g., vaccines, surgeries) or smoking/substance use history. All medication (e.g., prescription drugs, OTC drugs, herbal/homeopathic remedies, nutritional supplements) used by the patient within 4 weeks leading up to the screening visit will be collected.
- Physical examination: a general physical examination will be performed.
- Vital signs: including temperature, HR, respiratory rate, orthostatic SBP and DBP.
- ECG-12 lead.
- Serology: HIV (specific tests HIV-1 antibody), Hepatitis B (HBsAg, HBsAb) and hepatitis C virus (HCV) antibody.
- Pregnancy test (urine) in females.
- SARS-CoV-2 test (nasal swab, saliva).
- Substance abuse history, and test urine
- Blood sampling for hematology, chemistry, and coagulation.
- Urine sampling for urinalysis.
- Alcohol (urine test).
- Suicidality assessment.
- ABC-C test.
- SRS-2 test.
- SB5 ABIQ test.
- OACIS-severity assessment.
- NIH toolbox assessment.
- KiTAP assessment.
- CSHQ assessment.
- CGI-S assessment.
- AEs
- Previous and concomitant treatments.

Treatment period

The treatment period consists of 3 visits (Days 1, 7 and 14). After screening assessments, the enrolment and treatment period will be started. Patients meeting all inclusion and none of the exclusion criteria will be enrolled.

Patients will then receive the study medication, orally, twice daily (6 hours apart) for 14 days. The patient will be closely observed during and after the administration of the study medication. The following procedures and assessments will be performed during and after the treatment: Please refer to the Schedule of Assessment ([Appendix 1](#)).

Visit 2 (Day 1)

During the Day 1 visit, defined as the first day of the study drug administration, the following assessments will be performed:

- Randomization.
- Physical examination: a general physical examination will be performed.
- Vital signs: including temperature, HR, respiratory rate, SBP and DBP.
- Orthostatic BP assessment.
- ECG-12 lead.
- Substance abuse history, and test (urine)
- Hearing assessment.
- Administration of the study medication.
- Study medication supply.
- Blood and urine sampling for PK.
- Suicidality assessment.
- [REDACTED]
- KiTAP assessment.
- Eye tracking assessment (pre- and post-dose).
- EEG (pre- and post-dose).
- CSHQ assessment.
- AEs.
- Previous and concomitant treatments.

Visit 3 (Day 7)

- Physical examination: a general physical examination will be performed.
- Vital signs: including temperature, HR, respiratory rate, SBP and DBP.
- Orthostatic BP assessment.
- ECG-12 lead.
- Blood sampling for hematology, chemistry and coagulation .
- Urine sampling for urinalysis.
- Administration of the study medication.
- Blood sampling for PK at pre-AM dose.
- Suicidality assessment.
- Hearing assessment.
- AEs.
- Previous and concomitant treatments.

Visit 4 (Day 14)

- Physical examination: a general physical examination will be performed.
- Vital signs: including temperature, HR, respiratory rate, SBP and DBP.
- Orthostatic BP assessment.
- ECG-12 lead.
- Blood sampling for hematology, chemistry, and coagulation.
- Urine sampling for urinalysis.
- Administration of the study medication.
- Blood and urine sampling for PK
- Suicidality assessment.
- ABC-C test.

- SRS-2 test.
- OACIS-severity assessment.
- OACIS-change assessment.
- [REDACTED]
- KiTAP assessment.
- Eye tracking assessment.
- EEG.
- CSHQ assessment.
- CGI-I assessment.
- CGI-S assessment.
- Hearing assessment.
- AEs.
- Previous and concomitant treatments.

Visit 4 (Day 15) and optional visit 5/6/7 (Day 16/17/18) (adults)

Patients will be given the option to have their follow-up PK sampling visit between Day 16 and Day 18.

- Blood sampling for PK.
- Urine sampling for PK (visit 4 [Day 15] only).
- Suicidality assessment.
- AEs.
- Previous and concomitant treatments.

End-of-study (EOS) follow-up visit (visit 8, Day 28)

The following assessments will be performed for each patient on Day 28, at the end of the follow-up:

- Physical examination: a general physical examination will be performed.
- Vital signs: including temperature, HR, respiratory rate, SBP and DBP.
- Orthostatic BP assessment.
- ECG-12 lead.
- Pregnancy test (urine) in females.
- Blood sampling for hematology, chemistry, and coagulation.
- Urine sampling for urinalysis.
- Blood sampling for PK at any time.
- Suicidality assessment.
- ABC-C test.
- SRS-2 test
- [REDACTED]
- KiTAP assessment.
- Eye tracking assessment.
- EEG.
- CSHQ assessment.
- CGI-I assessment.
- CGI-S assessment.
- Hearing assessment.
- AEs.
- Previous and concomitant treatments.

At visit days when multiple assessments involving the patient coincide, the following sequence should be followed:

- Vital signs and ECG recordings.
- Fasting laboratory samplings (and PK sampling where applicable).
- Break.
- EEG and eye tracking recordings (on Day 1 only).
- Break, snack and dose administration.
- Cognitive assessment.
- EEG and eye tracking recordings.

The cognitive testing should be performed at a similar time of day and in the same sequence across all study visits. Breaks can be allowed between the cognitive tasks if deemed necessary by the clinician/rater.

4.6.2.1 SCREENING AND PRE-TREATMENT ASSESSMENTS

Written informed consent for participation in the study must be obtained before performing any study-specific screening tests or evaluations. Informed Consent Forms (ICFs) for enrolled patient and for patients who are not subsequently enrolled will be maintained at the study site.

All screening and pre-treatment assessments must be completed and reviewed to confirm that patients meet all eligibility criteria. The investigator will maintain a screening log to record details of all patients screened and to confirm eligibility or record reasons for screening failure.

An Eligibility Screening Form (ESF) documenting the investigator's assessment of each screened patient with regard to the protocol's inclusion and exclusion criteria is to be completed by the investigator and kept at the investigational site. Where the clinical significance of an abnormal screening test result (e.g., laboratory test) is considered uncertain, the test should be repeated to confirm the result.

Subjects who participated in the observational study [[STP1-C003, NCT04273087](#)] will not have to redo the ASD-Phen1 semi-structured interview form. Data from the STP1-C003 study will be transferred or entered into this study database.

An abbreviated rescreening may be allowed under circumstances where the patient is screen-passed but could not be randomized within the 2-week screening window due to a study halt, logistical, personal or technical reasons. At no time should the duration between the original screening visit and the abbreviated rescreening visit exceed 2 months, otherwise a full screening visit will be required. The abbreviated rescreening will include the following: a written informed consent, updated medical history, physical examination, drugs of abuse, pregnancy test (females only), alcohol urine test, laboratory safety, coagulation, viral serology, urinalysis, and inclusion/exclusion criteria.

4.6.2.2 ASSESSMENTS DURING TREATMENT

All assessments must be performed according to the Schedule of Assessments ([Appendix 1](#)). Under no circumstances will patients who enroll in this study and have completed treatment as specified, be permitted to be allocated a new randomization number and re-enroll in the study within the same cohort.

4.6.2.3 FOLLOW-UP ASSESSMENTS

Patients who complete the Day 15 study visit or discontinue from the study early, will be asked to return to the clinic on Day 28 (± 2 days) for the follow-up visit. After the study completion, AEs should be followed as outlined in [Section 5.6](#).

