If a patient experiences an AE that is judged to be related to the study drug, and is graded as mild or moderate, the patient may receive a further dose of study drug following discussion with the investigator and sponsor, dependent on the nature of the AEs reported. Expected transient GI pain requiring 48 hours stop and not resuming with reinitiation of treatment is commonly observed. The number of subjects reporting similar AEs and reports of the same or similar AEs in a patient, will form part of the assessment to determine if patients should be re-challenged.

Changes in vital signs and ECG intervals

Patients will be discontinued if after repeated measurements, have pulse/heart rate, blood pressure or ECG interval measurements that fulfil one or more of the criteria listed below.

Vital signs

- Pulse/heart rate <40 or >120 beats per minute (BPM)
- Systolic BP <90 or >180 mm Hg
- Diastolic BP <50 or >100 mm Hg

Laboratory tests

- Severe hypokalemia (defined as less than 2.5 mEq/L) or persistent hypokalemia despite potassium supplementation
- Thrombocytopenia is defined as meeting one or both criteria:
 - Platelet count below $150 \times 10^9/L$ (or 150.000 platelets per microliter (mcL))
 - Platelet count drop of $\geq 50\%$ compared to baseline
- Severe drug-induced liver injury (DILI).
- Dehydration and orthostasis (defined by a fall in systolic blood pressure over 20 mm Hg or a fall in diastolic pressure over 10 mm Hg within 3 minutes of standing).

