- ECG and vital signs data (including orthostatic blood pressure changes).
- Data quality, completeness and timeliness.
- Adherence to the protocol.

The DSMB will specifically assess the changes from baseline all safety laboratory data with a more specific evaluation of potential electrolyte imbalance and coagulation parameters.

The DSMB will provide recommendations to STALICLA as to whether the study should continue according to the protocol (i.e., proceeding with the recruitment for the second dose level of [REDACTED] mg twice a day (6 hours apart) of [REDACTED] mg twice a day (6 hours apart) of [REDACTED]) or be terminated.

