4.6.1.5 LABORATORY ASSESSMENTS

Normal ranges for the study laboratory parameters must be supplied to the sponsor before the study starts. Laboratory safety tests shall be collected at time-points specified in the Schedule of Assessments ([Appendix 1](#)).

Additional blood or urine samples may be taken at the discretion of the investigator if the results of any test fall outside the reference ranges, or clinical symptoms necessitate additional testing to monitor patient's safety. Where the clinical significance of abnormal laboratory results is considered uncertain, screening laboratory tests may be repeated before randomization to confirm eligibility. If there is an alternative explanation for a positive urine or blood test for drugs of abuse, e.g., previous occasional intake of a medication or food-containing for example, codeine, benzodiazepines or opiates, the test could be repeated to confirm washout.

In the event of unexplained abnormal clinically significant laboratory test values, the tests should be repeated immediately and followed up until they have returned to the normal range and/or an adequate explanation of the abnormality is found. Results of clinical laboratory testing will be recorded on the eCRF or be received as electronically produced laboratory reports submitted directly from the local or central laboratory.

When a fasted state is required, subjects have to be fasted for at least 4 hours.

Blood samples for the following laboratory tests will be sent to the local laboratory(ies) for analysis.

- Hematology (5 mL per sample): hemoglobin, hematocrit, erythrocytes, platelet count, leucocytes differential (absolute) counts (neutrophils, eosinophils, lymphocytes, monocytes, basophils).

- Blood chemistry (5 mL per sample): C-reactive protein (CRP test), AST, ALT, GGT, total and conjugated bilirubin, alkaline phosphatase (ALP), lactate, pyruvate, albumin, creatine phosphokinase (CPK), creatinine, urea, total protein, total cholesterol, triglycerides, sodium, chloride, calcium, magnesium, phosphate, potassium, glucose.
- Coagulation (2 mL per sample): international normalized ratio (INR), activated partial thromboplastin time (aPTT), prothrombin test (PT).
- Viral serology (2 mL per sample):
 - HIV (specific tests HIV-1 antibody).
 - Hepatitis B surface antigen (HBsAg).
 - Total hepatitis B core antibody (HBcAb).
 - Hepatitis C virus (HCV) antibody.

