4.7 PATIENT, STUDY, AND SITE DISCONTINUATION

4.7.1 PATIENT DISCONTINUATION

The investigator has the right to discontinue a patient from STP1 or withdraw a patient from the study at any time. In addition, patients have the right to voluntarily withdraw from the study at any time for any reason. Reasons for discontinuation of STP1 or withdrawal from the study may include, but are not limited to, the following:

- Patient withdrawal of consent at any time.
- Any medical condition that the investigator or sponsor determines may jeopardize the patient's safety if he or she continues in the study.
- Investigator or sponsor determines it is in the best interest of the patient.
- Patient non-compliance.

Patients who fulfill the criteria described in the Stopping Rules section (as defined in [Section 3.1.2](#)) should be discontinued from the study.

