5.5 FOLLOW-UP OF PATIENTS AFTER ADVERSE EVENTS

5.5.1 INVESTIGATOR FOLLOW-UP

The investigator should follow each AE until the event has resolved to baseline grade or better, the event is assessed as stable by the investigator, the patient is lost to follow-up, or the patient withdraws consent. Every effort should be made to follow all SAEs considered to be related to study drug(s) or trial-related procedures until a final outcome can be reported.

During the study period, resolution of AEs (with dates) should be documented on the AE eCRF page and in the patient's medical record to facilitate source data verification. If, after follow-up, return to baseline status or stabilization cannot be established, an explanation should be recorded on the AE eCRF page.

All pregnancies reported during the study should be followed until pregnancy outcome and reported according to the instructions provided in [Section 5.4.3](#).

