11. APPENDIX 1 SCHEDULE OF ASSESSMENTS

PERIOD	SCREENING	TREATMENT PERIOD			FOLLOW-UP VISITS	
		Day 1	Day 7	Day 14	Day 15-18 ^e	Day 28
Visit Window		+/-1	+/-1	+/-1	+/-2	
Assessments						
Informed Consent	x					
Eligibility	x					
Randomization		x				
Demography	x					
Medical History	x					
Physical Examination	x	x	x	x		x
Vital Signs	x	x ^a	x	x ^a		x
Orthostatic BP	x	x ^a	x	x ^a		x
ECG-12 Lead	x	x ^a	x	x ^a		x
Hearing Assessment		x	x	x		x
Serology	x					
Pregnancy Test (urine) ^b	x					x
SARS-CoV-2 Test (nasal swab, saliva)	x					
Substance Abuse (urine test)	x	x				
Blood Chemistry	x		x	x		x
Hematology	x		x	x		x
Coagulation	x		x	x		x
Urinalysis	x		x	x		x
Alcohol (urine test)	x					
Administration of Study Medication ^c		x	x	x		
Study medication supply		x				
Drug Accountability			x	x		x ^f
Blood PK Sample ^d		x	x	x	x	
Urine PK Sample ^d		x		x		
Suicidality (C-SSRS, C-CASA)	x	x	x	x	x	x
ABC-C	x			x		x
SRS-2	x			x		
SB5 ABIQ	x					
OACIS-Severity	x			x		
OACIS-Change				x		
████████	x	x		x		x
KiTAP	x	x		x		x
Eye Tracking		x		x		x
EEG		x		x		x
CSHQ	x	x		x		x
CGI-I				x		x
CGI-S	x			x		x
Adverse Events	x	x	x	x	x	x
Previous and Concomitant Treatments	x	x	x	x	x	x

a To be performed pre-dose and between 4 and 5 hours post-dose as specified in the protocol.

b Females only.

c Patients will receive their AM and PM dose of study drug during the Day 1, Day 7 and Day 14 visits to allow for proper PK sampling.

d PK samples will be collected as described in the PK assessment section. A 5 minutes window for each timepoint is allowed

e Day 16 to Day 18 are optional

f If not done at Day 14 visit

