Patients enrolled under Version 2 or 3 of the protocol will have blood and urine PK sampling done 30 hours post Day 14 AM dose (i.e., Day 15). Patients enrolled under Version 4 or subsequent versions of the protocol will be given the option to have their follow-up blood PK sampling visit between Day 16 and Day 18.

- Blood and urine sampling for PK (urine sampling collected for only those patients enrolled under Version 2 or 3 of the protocol)
- Suicidality assessment (C-SSRS, C-CASA) (collected for only those patients enrolled under Version 4 or subsequent versions of the protocol)
- AEs
- Previous and concomitant treatments

Visit 9- Day 28 - End of Study Follow-Up Visit

Patients who complete the Day 15 study visit or discontinue from the study early will be asked to return to the clinic on Day 28 (\pm 2 days) for the Follow-up visit. After study completion, AEs should be followed according to the study protocol.

The following procedures will be performed:

- Physical examination
- Vital Signs: including temperature, HR, respiratory rate, and BP
- Orthostatic BP assessment
- ECG-12 lead
- Pregnancy Test (urine) in females
- Blood sampling for hematology, blood chemistry, and coagulation
- Urine sampling for urinalysis
- Drug accountability (if not done at Day 14 visit for only those patients enrolled under Version 4 or subsequent versions of the protocol)
- Blood sampling for PK (collected for only those patients enrolled under Version 2 or 3 of the protocol)
- Perform study-specific assessments: Suicidality (C-SSRS, C-CASA), ABC-C, SRS-2, [REDACTED], KiTAP, CSHQ, CGI-I, and CGI-S
 - C-SSRS is collected for only those patients enrolled under Version 4 or subsequent versions of the protocol. SRS-2 is collected for only those patients enrolled under Version 2, 3, or 4 of the protocol.
 - Hearing assessment (collected for only those patients enrolled under Version 4 or subsequent versions of the protocol)

- Eye tracking assessment
- EEG
- Adverse Events
- Previous and Concomitant treatments

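### No early-termination visit is defined: beyond event-driven follow-up, a patient discontinued early is next scheduled at Day 28 (±2), nominally 15 to 27 days after the last dose

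*Protocol*

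**What the plan says.** **Who leaves the study.** Protocol 4.7.1: "Patients who fulfill the criteria described in the Stopping Rules section" should be discontinued from the study.

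**What they are scheduled for.** Protocol 4.6.2.3 covers patients who complete Day 15 and those who "discontinue from the study early, will be asked to return to the clinic on Day 28" (±2 days). SAP 1.2 has the same rule: patients who "discontinue from the study early will be asked to return to the clinic on Day 28". The table headed "11. APPENDIX 1 SCHEDULE OF ASSESSMENTS" has columns for screening, Days 1, 7 and 14, Days 15-18 and Day 28, and none for early termination. The visit lists in 4.6.2 have none either. Section 4.7.1.1 asks patients who stop STP1 early to attend a follow-up visit, gives no timing, and points to Section 4.6.2.4, which does not exist.

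**What is triggered by events.** Section 3.1.2: "Patients will be discontinued if after repeated measurements, have pulse/heart rate, blood pressure or ECG interval measurements" beyond the stated limits. Section 4.6.1.5 requires unexplained, clinically significant laboratory values to be repeated at once and followed. Otherwise, "Additional blood or urine samples may be taken at the discretion of the investigator". Section 5.5.1: "The investigator should follow each AE until the event has resolved to baseline grade or better", or is stable.

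**What is tied to the last dose instead.** The synopsis (Study Duration), 3.1.1, 5.3.1 and 5.6 put the follow-up visit, the follow-up phase or the end of adverse event reporting two weeks after the last dose.

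**How by-visit results are tabulated.** SAP 2.3 says analyses use observed data only. The footnotes to Tables 18, 19, 24, 30 and 31 use the whole Safety population as denominator, and these shells have no n per visit.

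**The concern.** Safety and tolerability is the primary objective. A patient who leaves early, particularly on a stopping rule, is where a safety signal is most likely to sit. The event-driven duties all respond to something already seen. None of them requires looking for an abnormality that has produced no symptom. Several adverse events of special interest are of that kind: 5.1.3 includes potassium below 3.4 mEq/L and platelets below 150 × 10⁹/L. A patient stopped for a severe related event between visits could leave with no potassium, platelet, creatinine or liver value taken near exposure, unless the investigator chose to sample.

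The dose-escalation decision draws on these data. Under 3.1.3, "The DSMB will specifically assess the changes from baseline all safety laboratory data with a more specific evaluation of potential electrolyte imbalance" and coagulation parameters. There are up to 6 active patients per dose and possibly only 3 at the high dose, so one missing on-drug panel is a large share of the evidence. The table denominators then make missing values harder to see.

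**Working it through.** **Inputs.** Planned last dose: morning of Day 14 (synopsis). Follow-up visit: Day 28, window Day 26 to Day 30 (4.6.2.3). Chemistry, hematology and coagulation: screening (Day -14 to -1), Day 7 (±1), Day 14 and Day 28 (Appendix 1). Laboratory baseline: screening (SAP 4.2). Half-lives: about 19 h for ibudilast and 0.7 to 1.5 h for bumetanide (1.4.1).

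**The plan's own interval.** 28 − 14 = 14 days, matching the stated two weeks.

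**Early stop, last dose on Day d (1 to 13).** Days to the visit = 28 − d.

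| Last dose | Nominal Day 28 | With ±2 window | Last dose + 14 days |
|---|---|---|---|
| Day 1 | 27 | 25 to 29 | Day 15 |
| Day 7 | 21 | 19 to 23 | Day 21 |
| Day 13 | 15 | 13 to 17 | Day 27 |

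A reporting period ending at last dose + 14 days therefore closes 28 − (d + 14) = 14 − d days before nominal Day 28, which is 13 days for d = 1 and 1 day for d = 13. With the window the gap reaches 30 − 15 = 15 days. The order can also reverse: for d = 13 a visit on Day 26 falls one day before Day 27.

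**Laboratory gap, leaving before Day 7.** The first scheduled post-dose panel moves from Day 7 to Day 28, 28 − 7 = 21 days later (26 − 8 = 18 to 30 − 6 = 24 with both windows). With no Day 0, the change from baseline spans 1 + 27 = 28 to 14 + 27 = 41 days, against 1 + 6 = 7 to 14 + 6 = 20 as planned.

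**Laboratory gap, leaving between Day 7 and Day 14.** The patient has the Day 7 panel. The next is 28 − 14 = 14 days later than the missed Day 14 panel.

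**Is the Day 28 value informative about exposure?** The shortest nominal gap is 15 days = 360 h: 360/19 = 18.9 ibudilast half-lives and 360/1.5 = 240 bumetanide half-lives. At the shortest gap with the window, 13 days = 312 h: 312/19 = 16.4 and 312/1.5 = 208. Drug is gone in every case. Completers also have a washout value at Day 28, but alongside Day 7 and Day 14 values.

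**Denominators (before any replacement).** Suppose one patient has no value at a visit and one other is abnormal. With 6 active patients the table prints 1/6 = 16.7% instead of 1/5 = 20%. With 3 it prints 1/3 = 33% instead of 1/2 = 50%.

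**How many patients.** The plan's 20% dropout reproduces its sample size: 16/0.8 = 20, so 4 of 20 leave. If dropout is equal by arm (assumption), that is 20% × (20 × 3/4) = 3 of 15 on active. The rate is all-cause and includes consent withdrawals, whom 4.7.1.2 bars from follow-up, so these are upper bounds at that rate. No rate of toxicity stops is given.

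**The case against.** The strongest reply is that a stopped patient is not left unexamined, and much of it stands. Vital-sign and ECG stops rest on repeated measurements. A laboratory stop rests on a laboratory value. Unexplained significant values must be repeated immediately, which is not discretionary. Adverse events are followed to resolution or stability, and serious events and those of special interest are reported within 24 hours. A stop made at the Day 7 visit coincides with that visit's full assessments. A reader might infer that no safety assessment at all is mandated for a patient stopped under 3.1.2; the documents do not support that. What they lack is the rest of the panel, and any requirement for a patient stopped on symptoms between visits.

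A reader might also see a conflict between 5.3.1 and 5.6. There is none: both give last dose + 14 days. The conflict is between those sections, with the synopsis and 3.1.1, and the fixed Day 28 of 4.6.2.3 and SAP 1.2. Someone following the first group could schedule an early stopper's visit at 14 days, so 15 to 27 days is the interval under 4.6.2.3, not under every section.

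Nor do the shift tables count a missing patient as normal. In Tables 18, 19 and 30 normal-to-normal is its own cell, and a missing patient falls in no cell, so the cells sum to less than N. Table 31, with only Low and High rows, is where the absence is hidden. Tables 17 and 20 do show n by visit, and listings and per-patient plots show individual values.

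Three further limits are fair. Early hypokalemia before Day 7 could be missed in any patient, since nobody has scheduled laboratory tests between the first dose and Day 7. Early stoppers may be replaced, and they remain in the adverse event tables. An early-termination sample does not guarantee an on-drug value: at 24 hours, 24/1.5 = 16 bumetanide half-lives have passed, against 24/19 = 1.3 for ibudilast. The documents give no recovery times for potassium, platelets or liver tests.

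**Conclusion.** The point holds in this form: no early-termination visit or fixed set of safety assessments is defined, and beyond event-driven duties the only visit scheduled for a patient discontinued from the study early is Day 28 (±2). The interval rests on reading 4.6.2.3 and SAP 1.2 as the operative rule; four other parts of the protocol use two weeks after the last dose, and that inconsistency is part of the finding. The main loss is laboratory: a patient who leaves before Day 7 has no scheduled on-drug value, and the only scheduled change from baseline is a washout one.

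The denominator issue is separate and adds no weight to the visit gap. It contradicts SAP 2.3 and lowers printed percentages whenever a value is missing, most seriously in Table 31. The wrong cross-reference in 4.7.1.1 is clerical. The change should be made because the primary objective is safety, the groups are very small and the remedy is cheap. The number of patients affected is unknown, with 4 of 20 as the upper bound at the planned dropout rate.

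**What to change.** 1. Add an Early Termination column to Appendix 1 with the existing Day 14 safety assessments: laboratory tests, ECG, vital and orthostatic signs, hearing and suicidality. Perform it as soon as possible after the last dose, for example within 24 to 48 hours, in patients who have not withdrawn consent. The time limit matters because a late visit would again be a washout sample.
2. Keep the Day 28 visit. State in the synopsis, 3.1.1, 4.6.2.3, 5.3.1 and 5.6 that adverse events are collected until that visit or last dose + 14 days, whichever is later. Correct the reference in 4.7.1.1 to 4.6.2.3.
3. In SAP Tables 18, 19, 24, 30 and 31, use patients with a value at the visit as the denominator (baseline and visit values for shift tables), show n, and add an early-termination or unscheduled row.

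Cost: one extra visit of existing procedures per early stopper, standing in for a missed Day 7 or Day 14 visit; a protocol amendment with IRB approval (9.5) and a consent update (8.2); edits to five table shells. No additional patients.
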